6.5.3.7. Dose interruptions

Applicable to encorafenib (Sub-Study A), binimetinib (Sub-Study A), and axitinib (Sub-Study B)

An interruption is defined as a 0 mg dose administered on one or more days for encorafenib, binimetinib, or axitinib. What follows defines how dose interruptions will be counted in the case of multiple dose interruptions.

- If an interruption occurs consecutively for at least two days, then it will be counted only once (example: If the actual dose on days 1-3 is 30 mg and actual dose on days 4-5 is 0 mg and dose interruption on days 4-5 is due to AE, then the total number of dose interruptions is 1).
- If an interruption occurs for more than one day but the days are not consecutive, ie there is at least one dosing day in between, then each dose interruption will be counted as a different occurrence (example: If the actual dose on days 1, 3 and 5, is 30 mg and actual dose on days 2 and 4 is 0 mg the total number of dose interruptions is 2).

A dose interruption is not considered a dose reduction.

The number and percentage of participants with dose interruptions and the corresponding reasons will be summarized.

6.5.3.8. Dose delays

Applicable to sasanlimab and SEA-TGT (Sub-Study B).

Dose Delay is the difference between the actual time between two consecutive non-zero doses and the planned time between the same two consecutive non-zero doses. ‘Unknown’ dose amounts for sasanlimab are considered a non-zero dose.

- Sub-Study A: Dose Delay for Dose x (days) = Date of Dose x – Date of Dose (x-1) – 28

- Sub-Study B: Dose Delay for Dose x (days) = Date of Dose x – Date of Dose (x-1) – 21
Dose delays will be grouped into the following categories:

- No delay
- 1-2 days delay
- 3-6 days delay
- 7 or more days delay

For example, for sasanlimab, administered on a 4-week schedule, if one participant receives sasanlimab on Day 1, then the next sasanlimab administration date will be on Day 29 however, if the participant receives sasanlimab at Day 30 or 31 this is considered as 1-2 days delay.

No delay and 1-2 days delay will also be summarized together.

The number and percentage of participants with delayed study drug administration and maximum length of delay, i.e., the worst case of delay if participants have multiple dose delays will be summarized.

6.5.4. Concomitant medications and non-drug treatments

The following analyses will be based on the safety analysis set by treatment group.

Concomitant medications are medications, other than study drugs, which started prior to first dose date of study treatment and continued during the on-treatment period as well as those started during the on-treatment period. **Prior medications** are medications, other than study drugs and pre-medications for study drug, which are started before the first dose of study treatment.

Concomitant medications will be summarized from the ‘Concomitant Medications’ eCRF page.

Summary of concomitant medications will include the number and percentage of participants by Anatomical Therapeutic Chemical (ATC) Classification level 2 and preferred term. A participant will be counted only once within a given drug class and within a given drug name, even if he/she received the same medication at different times. If any concomitant medication is classified into multiple ATC classes, the medication will be summarized separately under each of these ATC classes. The summary tables will be sorted on decreasing frequency of drug class and decreasing frequency of drug name in a given drug class. In case of equal frequency regarding drug class (respectively drug name), alphabetical order will be used. In case any specific medication does not have ATC classification level 2 coded term, it will be summarized under ‘Unavailable ATC classification’ category.

6.5.5. Subsequent anti-cancer therapies

The following analyses will be based on the full analysis set by treatment group.

Anti-cancer drug treatment will be provided in a data listing with data retrieved from 'Follow-up Cancer Therapy' eCRF page.

Number and percentage of participants with any anti-cancer therapy after discontinuation will be tabulated overall and by type of therapy based on the data collected from the 'Follow-up Cancer Therapy', 'Radiation Therapy' and 'On Study and Follow-up Cancer Surgery' eCRF pages.

6.6. Safety Summaries and Analyses

The Safety Analysis Set will be the primary population for safety evaluations. Summaries of AEs and other safety parameters will be based on the safety analysis set by treatment group.

6.6.1. Adverse events

Treatment-emergent adverse events (TEAEs) are those events with onset dates occurring during the on-treatment period as defined in Section 3.5.1.

All analyses described will be based on TEAEs (started during the on-treatment period) if not otherwise specified. The AE listings will include all AEs (whether treatment-emergent or not). AEs outside the on-treatment period will be flagged in the listings.

- **Related Adverse Events:** adverse events with relationship to study treatment (as recorded on the AE eCRF page, Relationship with study treatment = Related) reported by the investigator and those of unknown relationship (i.e., no answer to the question 'Relationship with study treatment'). Related AEs are those related to any study drug (i.e., at least one of the study drugs).
- **Serious Adverse Events (SAE):** serious adverse events (as recorded on the AE eCRF page, Serious Adverse Event = Yes).
- **Adverse Events Leading to Dose Reduction:** adverse events leading to dose reduction of study treatment (as recorded on the AE eCRF page, Action taken with study treatment = Dose reduced).
- **Adverse Events Leading to Interruption of Study Treatment:** adverse events leading to interruption of study treatment (as recorded on the AE eCRF page, Action taken with study treatment = Drug interrupted). The eCRF does not allow for a clear separation between interruption of an infusion and delays of administration for a parenteral drug as both are recorded using the same term on the eCRF ("Drug interrupted).
- **Adverse Events Leading to Permanent Treatment Discontinuation:** adverse events leading to permanent discontinuation of study treatment (as recorded on the AE eCRF page, Action taken with study treatment = Drug withdrawn).
- **Adverse Events Leading to Death:** adverse event leading to death (as recorded on the AE eCRF page, Outcome = Fatal, as well as AEs of Grade 5).
- **Immune-related Adverse Events (irAE):** irAEs (as identified according to the methodology outlined in Appendix 1 for a pre-specified search list of MedDRA PTs, documented in the Safety Review Plan [SRP] and finalized for analysis of the current study data prior to DB lock)

Unless otherwise specified, AEs will be summarized by number and percentage of participants with the AE in the category of interest as described above, by treatment group, primary SOC and PT in decreasing frequency based on the frequencies observed for Dose level 0 of Phase1b.

Each participant will be counted only once within each SOC or PT. If a participant experiences more than one AE within a SOC or PT for the same summary period, only the AE with the strongest relationship or the worst severity, as appropriate, will be included in the summaries of relationship and severity.

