3.5. Safety Endpoints

3.5.1. Adverse events

Treatment-Emergent Adverse Events

Treatment-emergent adverse events (TEAEs) are those events with onset dates occurring during the on-treatment period.

On-treatment period is defined as the time from the first dose of study treatment through minimum (30 days + last dose of study treatment, start day of new anti-cancer drug therapy – 1 day). The start day of new anti-cancer drug therapy after the first dose of study treatment is derived as outlined in Section 5.2.5.

Adverse Events of Special Interest (AESIs)

AESIs are immune-related adverse events (irAE). The criteria for classification of an AE as an irAE are described in Appendix 1.

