5.2.7. Definition of on-treatment period

Safety endpoints will be summarized based on the on-treatment period unless otherwise specified.

On-treatment period is defined as the time from the first dose of study treatment through minimum (30 days + last dose of study treatment, start day of new anti-cancer drug therapy – 1 day).

Safety data collected outside the on-treatment period as described above will be listed and flagged in listings but not summarized.

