6.6.3. Serious adverse events

The frequency (number and percentage) of participants with each of the following will be presented for treatment-emergent SAEs by treatment group:

- SAEs by SOC and PT

- Related SAEs by SOC and PT

The listings of all SAEs will also be provided with the relevant information with a flag for SAEs with onset outside of the on-treatment period.

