In addition, a listing of all TBILI, ALT, AST and ALP values for participants with concurrent (ALT or AST) $\geq 3 \times \text{ULN}$ and TBILI $\geq 2 \times \text{ULN}$ and (ALP $\leq 2 \times \text{ULN}$ or missing) will be provided.

Parameters with NCI-CTC grades available:

The laboratory toxicities will be tabulated using descriptive statistics (number of participants and percentages) during the on-treatment period. The denominator to calculate percentages for each laboratory parameter is the number of participants evaluable for CTCAE grading (ie those participants for whom a Grade 0, 1, 2, 3 or 4 can be derived).

- The shift table will summarize baseline CTCAE grade versus the worst on-treatment CTCAE grade. The highest CTCAE grade during the on-treatment period is considered as the worst grade for the summary.
- The number and percentage of participants with newly occurring or worsening laboratory abnormalities during the on-treatment period will be summarized by worst grade on-treatment (Grade 1, 2, 3, 4, Grade 3/4 and any grade [Grades 1-4]).

The above analyses apply to hematology and chemistry evaluations which can be graded per CTCAE.

Parameters with NCI-CTC grades not available:

Hematology and chemistry evaluations which cannot be graded per CTCAE criteria will be summarized as frequency (number and percentage) of participants with:

- shifts from baseline normal to at least one result above normal during on-treatment period
- shifts from baseline normal to at least one result below normal during on-treatment period

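### The TEAE definition has no worsening clause, so an AE recorded before first dose that worsens or becomes serious on treatment is left out of the TEAE tables if it stays under its original record

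*SAP*

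**What the plan says.** Section 3.5.1, repeated in Section 6.6.1, gives the definition: "Treatment-emergent adverse events (TEAEs) are those events with onset dates occurring during the on-treatment period". Section 5.2.7 sets the window: "On-treatment period is defined as the time from the first dose of study treatment through minimum" of two dates, namely 30 days after last dose and the day before a new anti-cancer drug therapy starts. The same section adds: "Safety data collected outside the on-treatment period as described above will be listed and flagged in listings but not summarized".

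Section 6.6.1 then fixes the default for the AE tables: "All analyses described will be based on TEAEs (started during the on-treatment period) if not otherwise specified". For serious events, Section 6.6.3 says that frequencies "will be presented for treatment-emergent SAEs by treatment group".

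The laboratory analysis in Section 6.6.5.1 works differently. It tabulates "participants with newly occurring or worsening laboratory abnormalities during the on-treatment period", by worst grade.

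**The concern.** In locally advanced or metastatic NSCLC, one way that toxicity can show itself is through a symptom already present at baseline becoming worse on study drug. A definition that looks only at the onset date does not recognise this. Take an event first recorded in screening at Grade 1 that reaches Grade 3, or becomes serious, after dosing. Its onset date stays before first dose if the site updates the existing record.

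Graded AEs are a stated secondary endpoint in both sub-studies. The rule can only remove events from the tables and cannot add any, so an error from this source understates toxicity. The laboratory tables do count worsening from baseline. A rise in ALT could therefore be counted there while the AE entered for it is missing from the AE tables.

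**Working it through.** No figure in the SAP depends on this definition, so the check follows one event through the plan.

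**Test case.** An AE starts on study day -3 at Grade 1. Under the same record it becomes Grade 4 and serious on day 20.

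| Place in SAP | Rule | Is the event counted? |
|---|---|---|
| 3.5.1, 5.2.7, 6.6.1 | Onset between first dose and end of window | No: onset precedes first dose, so it is not a TEAE |
| 6.6.1.1 | Overall, Grade 3 or higher, related and leading-to-death tables are of TEAEs | No |
| 6.6.1.2 to 6.6.1.4 | Dose reduction, interruption and discontinuation tables are of TEAEs | No |
| 6.6.3 | Frequencies for treatment-emergent SAEs | No |
| Appendix 1, Table 15, step 2 | Ignores TEAE status, but needs onset on or after first dose and within 90 days of last dose | Not by the algorithm |
| Appendix 1, closing text | Medical review may add cases that the algorithm misses | Possibly |
| 6.6.1 and 6.6.3 listings | All AEs and SAEs, flagged if outside the window | Yes, listed only |
| 6.6.2 | All deaths, with reason | Yes, if the event is fatal |
| 6.6.5.1 | New or worsening graded laboratory abnormality | Yes, if it is also a graded laboratory value |

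The worst-severity rule in Section 6.6.1.1 does not help, because it picks the highest grade among events already admitted to the table.

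**Missing onset dates.** Section 5.3.2.2 replaces a completely missing AE onset date by the start of treatment. An event of unknown timing therefore counts as treatment-emergent, while a documented on-treatment worsening of a pre-dose record does not.

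**Effect of one missed participant.** Arms B1, B2 and B3 of Sub-Study B have 20 participants each: 1/20 = 5 percentage points. Phase 2 of Sub-Study A has about 62: 1/62 = 1.6 percentage points. These figures show what one omission is worth. They do not estimate how many there will be.

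**The case against.** The strongest reply is that the loss depends on a recording convention that the SAP does not show. An event is omitted only if the baseline condition was entered as an AE with a pre-dose onset and its worsening stays under that record. Section 6.5.1.2 describes separate medical history pages. A condition held only there, and entered as a new AE when it worsens on treatment, would have an on-treatment onset and would count. Section 6.6.1 provides for more than one AE within a preferred term, and Section 6.6.1.3 for records of one term with different onsets. Such conventions are commonly left to the protocol or eCRF instructions. This stands as a limit on when the omission occurs. It does not remove the point: the SAP itself defines a TEAE, twice, by onset alone, and none of these sections says that a grade increase opens a new record.

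A second reply is that the laboratory rule is no contradiction, because worsening there is derived from repeated measurements against a baseline grade, whereas AE tables count investigator records. That is fair. The comparison shows that the SAP treats worsening as relevant in one place and is silent in the other.

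A reader might also infer that such an event vanishes from all safety output, deaths included. It does not. The listings keep it, Section 6.6.2 tabulates every death with its reason, and medical review can add an irAE.

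A reader might further infer that the recommended Phase 2 dose would be biased. The support for that is thin. Dose finding is guided by DLTs in DLT-evaluable participants. Other safety data may contribute under Sections 2.2.2 and 5.1.2.1, but that review is not confined to TEAE frequencies.

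**Conclusion.** The point holds as a gap in a stated definition. Where worsening of a pre-dose AE is kept under its original record, the event is missing from the TEAE frequency tables and is not selected by the irAE algorithm. Any resulting bias in the AE rates is downward. Primary endpoints, sample size and decision rules are unaffected.

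The size cannot be derived from the SAP, which gives no baseline symptom rates and no recording rule. One could assume that 10 to 30% of the 62 participants have an ongoing recorded AE at first dose and that 10 to 20% of those worsen to Grade 3 or higher. That gives 62 x 0.10 x 0.10 = 0.6 to 62 x 0.30 x 0.20 = 3.7 participants. Neither range has a source in the document. On these assumptions the result is a ceiling, since a participant with any other Grade 3 or higher TEAE is already counted in that rate. It should not be read as an expected loss. If every worsening opens a new record with its own onset date, the loss is zero.

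**What to change.** In Sections 3.5.1 and 6.6.1, define a TEAE as an event with onset in the on-treatment period, or an event present before first dose that worsens in grade or becomes serious in that period. Summarise such events at the worst on-treatment grade. Add the matching clause to step 2 of Table 15, applied to the window which that step already uses. If the eCRF instructions already require a new record with a new onset date at each worsening, stating that in the same two sections would do the same job.

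The cost is a wording change and one programming condition. Reported AE rates may become slightly higher.

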6.6.1.1. All adverse events

Adverse events will be summarized by worst severity (according to NCI-CTCAE version 5.0) per participant, using the latest version of MedDRA preferred term (PT) as event category and MedDRA primary system organ class (SOC) body term as Body System category.

In case a participant has events with missing and non-missing grades, the maximum of the non-missing grades will be displayed. No imputation of missing grades will be performed.

The following tables will be created:

- The overall summary of AEs table will include the frequency (number and percentage) of participants with each of the following by treatment group as applicable:
 - TEAEs
 - TEAEs, Grade ≥ 3
 - Related TEAEs
 - Related TEAEs, Grade ≥ 3
 - TEAEs leading to dose reduction of sasanlimab
 - TEAEs leading to dose reduction of encorafenib
 - TEAEs leading to dose dose reduction of binimetinib
 - TEAEs leading to dose reduction of axitinib
 - TEAEs leading to dose reduction of SEA-TGT
 - TEAEs leading to interruption of sasanlimab
 - TEAEs leading to interruption of encorafenib
 - TEAEs leading to interruption of binimetinib
 - TEAEs leading to interruption of axitinib
 - TEAEs leading to interruption of SEA-TGT
 - TEAEs leading to discontinuation of sasanlimab
 - TEAEs leading to discontinuation of encorafenib

- TEAEs leading to discontinuation of binimetinib
- TEAEs leading to discontinuation of axitinib
- TEAEs leading to discontinuation of SEA-TGT
- TEAEs leading to discontinuation of all study drugs
- Related TEAEs leading to discontinuation of sasanlimab
- Related TEAEs leading to discontinuation of encorafenib
- Related TEAEs leading to discontinuation of binimetinib
- Related TEAEs leading to discontinuation of axitinib
- Related TEAEs leading to discontinuation of SEA-TGT
- Related TEAEs leading to discontinuation of all study drugs
- Serious TEAEs
- Related Serious TEAEs
- TEAEs leading to death
- Related TEAEs leading to death
- irAEs
- TEAEs by SOC and PT and worst grade
- TEAEs related to any study drug by SOC and PT and worst grade
- TEAEs leading to death by SOC and PT
- Related TEAEs leading to death by SOC and PT

6.6.1.2. Adverse events leading to dose reduction

The frequency (number and percentage) of participants with each of the following will be presented for TEAEs leading to dose reduction of each study drug by treatment group as applicable:

- TEAEs leading to dose reduction of encorafenib by SOC and PT
- TEAEs leading to dose reduction of binimetinib by SOC and PT
- TEAEs leading to dose reduction of axitinib by SOC and PT
- TEAEs leading to dose reduction of SEA-TGT by SOC and PT

The listing of all AEs leading to dose reduction will also be provided with the relevant information.

6.6.1.3. Adverse events leading to interruption of study treatment

AEs leading to interruption will be defined as AEs identified in the AE eCRF page with an action taken with study treatment of ‘drug interrupted’.

The frequency (number and percentage) of participants with each of the following will be presented for TEAEs leading to interruption of each study drug by treatment group:

- TEAEs leading to interruption of sasanlimab by SOC and PT
- TEAEs leading to interruption of encorafenib by SOC and PT
- TEAEs leading to interruption of binimetinib by SOC and PT
- TEAEs leading to interruption of axitinib by SOC and PT
- TEAEs leading to interruption of SEA-TGT by SOC and PT

The listing of all AEs leading to interruption of study treatment will also be provided with the relevant information.

In addition, the frequency (number and percentage) of participants with each of the following will be presented for TEAEs leading to interruption of each study drug by treatment group:

- TEAEs leading to both interruption and dose reduction of encorafenib by SOC and PT
- TEAEs leading to both interruption and dose reduction of binimetinib by SOC and PT
- TEAEs leading to both interruption and dose reduction of axitinib by SOC and PT
- TEAEs leading to both interruption and dose reduction of SEA-TGT by SOC and PT

This summary will take into account PTs with both actions as defined in Section 6.6.1, even though the actions may be captured for different PT records (i.e., different onset for the PT with action “drug interrupted” and the PT with action “dose reduced”).

6.6.1.4. Adverse events leading to discontinuation of study treatment

The frequency (number and percentage) of participants with each of the following will be presented for TEAEs leading to permanent discontinuation of each study drug and study treatment, by treatment group:

- TEAEs leading to discontinuation of sasanlimab by SOC and PT
- TEAEs leading to discontinuation of encorafenib by SOC and PT
- TEAEs leading to discontinuation of binimetinib by SOC and PT
- TEAEs leading to discontinuation of axitinib by SOC and PT
- TEAEs leading to discontinuation of SEA-TGT by SOC and PT

- Related TEAEs leading to discontinuation of sasanlimab by SOC and PT
- Related TEAEs leading to discontinuation of encorafenib by SOC and PT
- Related TEAEs leading to discontinuation of binimetinib by SOC and PT
- Related TEAEs leading to discontinuation of axitinib by SOC and PT
- Related TEAEs leading to discontinuation of SEA-TGT by SOC and PT
- TEAEs leading to discontinuation of all study drugs by SOC and PT
- Related TEAEs leading to discontinuation of all study drugs by SOC and PT

The listing of all AEs leading to treatment discontinuation will also be provided with the relevant information.

6.6.2. Deaths

The frequency (number and percentage) of participants in the safety analysis set who died and who died within 30 days after last dose of study treatment as well as the reason for death, will be tabulated based on information from the ‘Notice of Death’ and ‘Survival Follow-Up’ eCRFs, by treatment group.

- All deaths
- Deaths within 30 days after last dose of study treatment
- Reason for Death
 - Disease under study
 - Study treatment toxicity
 - Unknown
 - Other.

In addition, date and cause of death will be provided in individual participant data listing together with selected dosing information (study treatment received, date of first / last administration, dose) and will include the following information:

- AEs with fatal outcome (list preferred terms of AEs with outcome=Fatal, as well as AEs of Grade 5),
- Flag for death within 30 days of last dose of study treatment.
- Flag for deaths related to COVID-19.

